4.7.6 Follow-up Assessments

During the clinic visit, we will audio-record clinical encounters with consented patients to assess the fidelity of intervention delivery (T1). After the visit, participants will be asked to complete a second questionnaire (T2). Two additional follow-up assessments will occur around 1-2 weeks (T3) and 12 weeks post- surgery (T4) (Fig. 5). For participants recruited in the first nine months of the trial, we will also conduct a follow-up assessment 1 year post-surgery (T5).

Follow up questionnaires will be administered in the clinic, when possible, and aligned with regularly scheduled return clinic visits. If this is not possible, follow-ups will be conducted either over the phone, online (sent as an email via REDCap), or on paper (sent via mail with a pre-stamped, self-addressed envelope).

To minimize respondent burden and disruption and to accommodate varying levels of literacy and health literacy, validated short-form questionnaires will be used. Each follow-up assessment (T2, T3, T4, and T5) comprises 10-34 items.

We expect that T0 (baseline assessment) will take between 15 and 30 minutes. All subsequent assessments will take approximately 10 minutes.

For each assessment, the outcome measures will be combined into one questionnaire to improve ease of use (see Table 4).

Table 4. Number of items according to data collection point

Measure	Number of Items	T0 Baseline	T2 Post-Visit	T3 1 Week Post-Surgery*	T4 12 Week Post-Surgery**	T5 1 Year Post-Surgery
Health literacy	1	X				
Demographic survey	6	X				
Decision quality	16		X	X		
Knowledge (5-item subscale of DQI)	5	X	(X)	(X)		

Treatment intention (self-reported)	1		(X)			
Quality of life	6	X			X	
Anxiety	8	X	X	X	X	
Shared decision-making (self-reported)	3		X			
Decision regret	5			X	X	X
Integration of healthcare delivery	4	X			X	
Financial toxicity	5			X	X	X
Total number of items		30	27	34	28	10

* or first post-operative visit

** or second post-operative visit

4.7.7 Monitoring Enrollment

The research assistant will closely monitor enrollment at each site on a weekly basis. The number of patients screened by the breast care team, proportion eligible (and sent an information sheet), and proportion consented and recruited in-clinic (according to SES strata) will be collected on a screening log. We plan to share information on recruitment numbers with the core team on a weekly basis and with each clinic every two weeks. Should a participant drop out, the research assistant will notify the breast care team who will review the electronic medical record to identify a potential reason for attrition. We will specifically monitor recruitment in the lower SES strata on a weekly basis. Should recruitment in this group prove slower than expected, we will solicit the advice and expertise of our patient partners, patient associates, and Community Advisory Board members to identify solutions and implement additional recruitment strategies.

4.7.8 Tracking and Retaining Participants

The research assistant or patient associate employed at each site will track participants and ensure that they are called in advance of the follow-up assessments and provided with a questionnaire in the format of their choice. Interpreter services will be used whenever necessary. Telephone calls will also be made by the patient associates whenever they are available.

Retention among patients of lower SES will be maximized by:

- Using short-form validated measures;
- Translating those measures into Spanish and simplified Mandarin Chinese;
- Using interpreter services whenever necessary;
- Calling (or emailing at Dartmouth) all participants three to five days before each follow-up assessment is due, prompting patients to complete the questionnaires and offering to conduct a standardized interview over the phone. The latter is likely to be particularly helpful in patients of lower SES and lower literacy/health literacy;
- Conducting follow-up assessments in-person when possible;
- Giving patients a choice of questionnaire format for the completion of baseline and follow-up assessments (online via email, paper-based, or standardized interviews);
- Compensating participants for their time: \$15 gift card at T2, T3, T4, and T5 for patients who complete the questionnaires. Brueton et al. identified monetary incentives as an effective way of improving participant retention¹¹⁴.

4.7.9 Training

All participating clinicians will receive training in using the intervention they are randomized to and in how to adhere to the trial protocol. The training will include basic communication and risk communication skills. We will use videos and role-plays. For clinicians who are not able to attend a training session in person, an online module and video will be available.

4.7.10 Adherence to Protocol and Supervision

To maximize adherence to the trial protocol, we will train all co-investigators, research assistants, and patient associates at each site in recruiting patients according to the procedures outlined in the protocol and will ensure that all principal stakeholders have received appropriate CITI training.

For the DQI adaptation interviews, the PI and research project coordinator will monitor adherence to the interview guide by reviewing the 1st and 5th interview transcript at each study site and providing feedback to the research assistants conducting interviews. We will follow the same process for the Aim 3 interviews.

In addition, the protocol will be made available to all research team members and key stakeholders in a password protected section of the website. We will provide supervision, feedback and additional training to clinicians and other study staff, as necessary at 3 months, 6 months, and 12 months into recruitment. Feedback will be provided using a preliminary analysis of the audio recordings of selected consultations across all three arms and field-notes.

4.7.11 Reporting Plan and Study Termination

Our reporting plan will diligently adhere to the updated guidelines set-out in the CONSORT 2010 statement for reporting randomized trials⁸⁷ and will be sufficiently transparent and comprehensive to allow for assessment of the study's internal and external validity.

For participants recruited in the first nine months of the study, the study will end after completing the T5 assessment (1 year post-surgery). For all other participants, the study will end 12 weeks post-surgery or after Aim 3 interviews have been conducted (where applicable). Depending on the participant, the Aim 3 interview will take place at T4 or T5. All participants will resume usual care once the study has ended.

4.8 Analysis

4.8.1 Power Calculation

For Aim 1, hypothesis 1, we base the effect size estimation on published data from randomized controlled trials of decision aids for breast cancer surgery^{32,41,115,116}, suggesting that a reasonable effect size for DQI is 9.34, that the standard deviation between patients in the intervention arms compared to usual care is 12.00, and that a within-physician intra-class correlation (ICC) of 0.05 is reasonable. This ICC is justified because treatment varies within clinic, thereby allowing heterogeneity that occurs between physicians across centers to be blocked. We assume that four physicians will participate in the study at each of the four clinics (at least one assigned to each of the three trial arms at each center) and assume a patient attrition rate of 20%. Under these assumptions, a study of 1,100 participants (68.75 participants per physicians and 366.66 per treatment group) has power of greater than 99.8%

to reject the null hypothesis that the encounter decision aid groups and the control group have equal means, using a two-sided 0.05 level test when the true mean difference is 9.34. Given recruitment difficulties due to seasonal trends in breast cancer diagnoses and a lower number of eligible patients than planned based on the feasibility assessments (see reasons in modification letter), the sample size has been revised to 600 participants. The power will remain above 80% for all primary hypotheses.

A crucial feature of this power calculation is that the design-effect equals 4.04, implying that approximately 4 times as many patients are needed to obtain the same power as for a study with patient-level randomization. Power remains above the traditional 80% threshold with an ICC greater than 0.19, implying that the power remains adequate even if the level of clustering of patients within physicians is greater than anticipated. Further, the attrition rate of 20% is expected to be an overestimate given the brevity of the trial. The standard deviation between patients' DQI values deliberately errs on the side of an overestimate; hence, power may be substantially greater. For hypothesis 2, we are basing the effect size estimation on the comparison between Picture Option Grid and Option Grid in women of lower SES. Because we anticipate obtaining a similar number of women in the higher and lower SES categories, the same power calculation is performed on a sample size of half the size. With 550 patients in total (34.375 patients on average per physician), under the same assumptions as above, the power for this subgroup test is 99% with ICC = 0.05 and 80% with ICC = 0.175.

For Aim 2, the power of the test for disparities between higher and lower SES is necessarily lower than the overall test at the same effect size, as four groups are compared (Picture Option Grid higher SES, Picture Option Grid lower SES, Option Grid and usual care higher SES, Option Grid and usual care lower SES). However, because patient SES varies within physician, power can be conservatively computed as if the patient-level variance was doubled and the total number of patients halved. If the true difference in the effect of the Picture Option Grid on DQI between the higher and lower SES groups is 8.5 compared to Option Grid or compared to usual care, the power for a two-sided alpha-level test at the 0.05-level is just above 80%. With a revised sample size of 600 participants, the power is unlikely to reach 80%. However, given those power calculations are resting on assumptions that may not be entirely accurate, we will know once we start the analysis if we have enough power for aim 2 hypotheses with a sample size of 600 participants. A significant finding is even more likely to be obtained if the estimated variability in the data turns out to be much smaller than assumed here. It could indeed be the case with the revised sample size. It is not critical to account for multiple testing because in both the primary (Aim 1) and secondary (Aim 2) analyses, a single pair of groups is compared.

We are assuming an effect size of 9.34 based on past studies of decision aids for breast cancer surgery^{32,41,115}.

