4.3.4 Feasibility of Recruitment

We aim to recruit 317 patients at Dartmouth-Hitchcock, Montefiore Medical Center, and Washington University in St. Louis (this number may vary depending on stratification and patient volume). Given the lower patient volume at NYU School of Medicine, we will aim to recruit 150 patients. At Dartmouth-Hitchcock, the screening exercise revealed that 339 women would have been eligible for participation in this study in 2014. This represents about 452 women potentially eligible over 18 months. At the Joanne Knight Breast Health Center (Washington University in St. Louis), 724 women would have been eligible to take part in the proposed study in 2014, representing approximately 965 eligible participants over 18 months. At Montefiore Medical Center, 443 women would have been eligible to take part in the proposed study in 2014. This represents a total of approximately 591 eligible participants over 18 months. Given a revised target sample size of 600 and varying recruitment by site, the per site enrollment will not reach these numbers, however we have accounted for this (see section 4.8 - Analysis).

Barriers to enrollment will be overcome by employing a research assistant and patient associate at each site throughout the study, by offering compensation for baseline and follow-up assessments, by informing participants of the study in advance of their surgical consultation, by developing materials with our patient and stakeholder partners using plain language and translations into Spanish and Mandarin Chinese, by offering several modes of questionnaire completion, and by working with our Community Advisory Board (see section

7.2 Conducting the Study for more detail on the Community Advisory Board) and patient and stakeholder partners to overcome potential issues with recruitment. We have allocated two extra months for the analysis and write-up of the findings, in case recruitment would need to be extended. We anticipate that the attrition rate will be minimal given the brevity of the trial, and will implement various strategies to maximize recruitment and retention.

Table 1. Recruitment Plan for the Randomized Controlled Trial

Estimated number of potentially eligible study participants	Based on administrative data: 2474
Total number of study participants expected to be screened	2400
Total number of study participants expected to be eligible	2200
Target sample size	600

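### Section 4.8.1 still carries the design effect and ICC limits for 1,100 patients; at 600 they do not hold, and Aim 2 has no power figure but an invalid argument about variability

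*Combined protocol and SAP*

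**What the plan says.** Section 4.8.1 (Power Calculation) sets out a calculation for 1,100 patients: effect 9.34 points, SD 12, within-physician ICC 0.05, four physicians at each of four clinics, 20% attrition, two-sided 0.05 test. It then lowers the sample to 600 because of recruitment difficulties and adds, without a figure: "The power will remain above 80% for all primary hypotheses".

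The next paragraph continues in the present tense with "the design-effect equals 4.04" and "Power remains above the traditional 80% threshold with an ICC greater than 0.19", and concludes that power is adequate even if clustering is stronger than expected. Hypothesis 2 is still computed on half of 1,100 (550 patients, 34.375 per physician), with the result that "the power for this subgroup test is 99% with ICC = 0.05 and 80% with ICC = 0.175".

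For Aim 2, the plan says power at 1,100 is just above 80% for a difference of 8.5 and is unlikely to reach 80% at 600. It gives no number. It says "we will know once we start the analysis if we have enough power for aim 2 hypotheses", and, on the possibility that variability is smaller than assumed, "It could indeed be the case with the revised sample size".

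Section 4.3.4 (Feasibility of Recruitment) notes the target of 600 and per-site enrolment below the earlier figures, and refers the reader to Section 4.8 for how this was taken into account.

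**The concern.** The trial randomizes about 16 surgeons, so its power depends heavily on the ICC. The ICC limits are the plan's evidence that the trial can tolerate more clustering than the assumed 0.05. If they belong to a larger trial, that assurance is overstated.

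Aim 2, the effect on disparities, is one of the three named aims. Without the planning power and detectable difference at 600, a null result cannot be read properly. Leaving the adequacy of power to be judged once the analysis starts does not replace a planning figure.

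Section 4.8.1 also says adjustment for multiple testing is not critical, while Section 4.8.3 adopts Scheffe's method. The rule under which any restated power would apply is therefore unsettled.

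**Working it through.** **Inputs (all from Section 4.8.1).** Difference 9.34 (Aim 1) or 8.5 (Aim 2); SD 12; ICC 0.05; S = 16 surgeons; attrition 20%; equal arms; two-sided 0.05.

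**Formulas.** Analysed patients per arm n = 0.8N/3. Analysed patients per surgeon m = 0.8N/16. Design effect DE = 1 + (m − 1) × ICC. SE = 12 × √(2 × DE/n). Power = Φ(difference/SE − 1.960). For the ICC limit, 80% power needs SE = 9.34/2.802 = 3.334, so DE = 3.334² × n/(2 × 144) and ICC = (DE − 1)/(m − 1).

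**Step 1: reproduce the plan at 1,100.**
- Hypothesis 1: n = 293.3, m = 55, DE = 3.70, SE = 1.906, power 99.84% (stated: greater than 99.8%). Limit: (11.32 − 1)/54 = 0.191 (stated 0.19).
- Hypothesis 2 (550): n = 146.7, m = 27.5, DE = 2.325, SE = 2.137, power 99.2% (stated 99%). Limit: (5.66 − 1)/26.5 = 0.176 (stated 0.175).
- Aim 2 (variance doubled, patients halved): SE = √2 × 2.137 = 3.02, power 80.3% (stated: just above 80%).

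All stated powers and limits reproduce, so this is the plan's method. The design effect does not: it is 3.70 at the stated 20% attrition and 4.39 with none. The value 4.04 needs 10% attrition (m = 61.875). This mismatch does not affect the stated powers.

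**Step 2: the same method at 600.**

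| | Hypothesis 1 (N = 600) | Hypothesis 2 (N = 300) |
|---|---|---|
| Enrolled per surgeon | 37.5 | 18.75 |
| Analysed per arm, per surgeon | 160, 30 | 80, 15 |
| DE at ICC 0.05 | 2.45 | 1.70 |
| SE | 2.100 | 2.474 |
| Power at ICC 0.05 | 99.4% | 96.5% |
| ICC limit for 80% | (6.174 − 1)/29 = 0.178 | (3.087 − 1)/14 = 0.149 |
| Limit quoted in the plan | 0.19 | 0.175 |
| Power at the quoted limit | 77.9% | 75.5% |

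Less attrition does not restore the quoted limits. With the 5% missing data expected in Section 4.8.7 they are 0.183 and 0.159; with no loss at all, 0.184 and 0.161.

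**Step 3: Aim 2 at 600.**
- SE = √2 × 2.474 = 3.499, which is 3.499/3.022 = 1.158 times the value at 1,100. Power for 8.5 points: Φ(8.5/3.499 − 1.960) = 68.1% (72.1% with 5% missing).
- Detectable difference at 80% power: 2.80 × 3.499 = 9.80.
- SD needed for 80% power at 8.5 points: 12 × 8.5/9.80 = 10.4.
- The plan calls this formula conservative. Assuming instead that surgeon variance cancels within surgeon, SE = 12 × √(0.95 × 8/160) = 2.615 and power is 90.1%.

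**Step 4: the variability argument.** Enrolling fewer patients does not lower the patient SD or the ICC. It does make clusters smaller and so lowers the design effect, but that is already in Step 3, and the SE still rises by 16%.

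**Step 5: sensitivity to multiplicity (hypothesis 2, ICC 0.05).** Under Scheffe's method with a normal reference, power is 86%, 91% and 93% for 12, 16 and 20 surgeons. With a t reference on an assumed S − 3 degrees of freedom it is 72%, 83% and 88%. These are not the plan's calculation; they show only that the choice of rule matters.

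**The case against.** - **The powers and ICC limits were correct for the sample they were computed for**, and the hypothesis 2 figures are openly tied to 550 patients. That is true. But they stand as the current justification after the cut to 600, and the 0.19 statement carries no such label.
- **The shift is modest.** Both limits at 600 remain about three times the planning ICC or more. The plan also says SD 12 is deliberately high; an SD of 11.7 (hypothesis 1) or 11.35 (hypothesis 2) would restore 80% at the quoted limits. This stands: the broad conclusion that the primary tests tolerate more clustering than expected survives. The specific limits do not, at the SD the plan uses.
- **Surgeon numbers matter more than the cut.** Section 4.1.2 allows three to five clinicians per site. At 600 the limits are 0.133 and 0.110 with 12 surgeons, and 0.225 and 0.190 with 20. This is a good reason to show the range, but Section 4.8.1 assumes 16.
- **Other groupings are more favourable.** Pooling the two aid arms gives a hypothesis 1 limit of 0.249 at 600. Pooling the Aim 2 comparators, as the four-group description suggests, gives 80.1%. At 1,100, however, these readings give a limit of 0.261 and Aim 2 power of 90%, not the stated 0.19 and just above 80%, so they are not the method used. The plan should still name its Aim 2 contrast.
- **The Aim 2 shortfall is already admitted, and the variability remark is conditional.** The admission stands. What is missing is the figure, and the link drawn between smaller variability and the revised sample size has no basis.
- **Section 4.3.4 refers to site enrolment, and Section 4.8 does mention 600.** True, but Section 4.8 shows no calculation for 600.
- **The multiplicity conflict did not arise from the cut.** Agreed; it matters here only because restated power depends on the rule.

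**Conclusion.** The point holds. The design effect of 4.04 and the ICC limits of 0.19 and 0.175 are wrong for the 600-patient trial: on the plan's inputs they are 2.45, 0.178 and 0.149. The value 4.04 also fails to match the stated 20% attrition at 1,100. Aim 2 has 68% power by the plan's own conservative formula, or about 90% if surgeon variance cancels within surgeon, and the argument about smaller variability is invalid.

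No primary power claim fails: at ICC 0.05 both primary hypotheses stay well above 80%. These results rest on 16 surgeons with equal caseloads, 20% attrition, SD 12, and pairwise normal tests without multiplicity adjustment.

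**What to change.** Restate Section 4.8.1 for 600 patients:
- 200 per arm and 37.5 per surgeon; design effect 2.45 at 20% attrition.
- Hypothesis 1: power 99.4% at ICC 0.05, ICC limit 0.178.
- Hypothesis 2: 300 patients, 18.75 per surgeon, power 96.5% at ICC 0.05, ICC limit 0.149.
- Aim 2, with the contrast named: 68% for 8.5 points by the conservative formula (about 90% if surgeon variance cancels within surgeon), detectable difference 9.8 at 80% power, SD of 10.4 or less needed for 80% at 8.5.

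Delete the sentence linking smaller variability to the revised sample size and the one leaving the adequacy of power to the analysis stage. Reconcile Sections 4.8.1 and 4.8.3 on multiplicity. As a sensitivity analysis, show power under the rule actually adopted, with a small-cluster t reference, for 12, 16 and 20 surgeons, and label the degrees of freedom as an assumption.

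The cost is text only. The design and sample size do not change, and neither do the planned models. The ICC limits become slightly less favourable, and the primary power statement stands with its figures shown.

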3.2 Aims and Objectives

The three specific aims will be realized in the context of the logic model shown in Fig. 3:

AIM 1: Assess the comparative effectiveness of two effective encounter decision aids (Option Grid and Picture Option Grid) against usual care on shared decision-making (SDM), decision quality, treatment choice and other direct outcomes in women, and differentially by socioeconomic status (SES).

Hypothesis 1. The encounter decision aids will increase SDM in the clinic visit and improve decision quality, knowledge, and quality of life in women of higher and lower SES compared to usual care. We also anticipate that they will reduce decision regret and improve the perceived integration of healthcare delivery (see Fig. 3).

Hypothesis 2. The Picture Option Grid will be more effective than the Option Grid at improving primary and secondary outcomes in women of lower SES. There will be no difference between the effects of the two encounter decision aids in women of higher SES.

AIM 2: Measure the effect of the Picture Option Grid on disparities in decision-making (decision quality, knowledge, and SDM) and treatment choice, and conduct an exploratory analysis of the mediation and moderation effects.

Hypothesis 1. Compared to the Option Grid and usual care arms, the Picture Option Grid will reduce disparities in decision quality, knowledge and participation in shared decision-making between women of lower and higher SES. It is also likely to reduce disparities in treatment choice.

Hypothesis 2. The effect of the Picture Option Grid on treatment choice will be mediated by post-intervention knowledge, shared decision-making, and post-intervention values (reported in 'What Matters Most to You' subscale of DQI, e.g., keeping breast, removing breast to gain peace of mind, avoiding radiation, etc.) (see Fig. 4).

[figure not shown]
Hypothesis 3. For women of lower SES, socioeconomic barriers (e.g., resource constraints, as reported in the Decision Quality Instrument) will affect treatment choice and thereby moderate the intervention's effect.

AIM 3: Explore strategies that promote the encounter decision aids' sustained use and dissemination using a theoretical implementation model.

Hypothesis 1. Pre-visit planning, minimal clinician training, flexibility of use, and integration into the workflow and EMR will facilitate sustained use.

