A logistic regression model will be used to test for differences in decision quality, knowledge, participation in SDM, and treatment choice between the Picture Option Grid group and the usual care and Option Grid groups, within subpopulations (higher SES versus lower SES). A reduction of disparity due to the interventions will be claimed if the effect of SES on outcomes is significantly smaller for the Picture Option Grid group than for the other two groups at follow-up. As for Aim 1, a linear regression model will be used for the decision quality analysis while an analogous set of other predictors will be included as covariates in the model. The assumptions of the models will be evaluated for adequacy using residual analysis and other model fit diagnostics¹²¹. Our exploratory mediation analyses seek to identify and explicate the mechanism or process that underlies the relationship between the Picture Option Grid and a dependent variable via the inclusion of a third explanatory variable, known as a mediator variable (e.g., knowledge, values, SDM). We are specifically interested in whether interventions operate through the mediator as opposed to directly affecting the outcome. We will perform these analyses even if the findings from Aim 1 and Aim 2 (hypothesis 1) are non-significant in order to determine whether the null effect was due to a null effect of the intervention on the mediator or a null effect of the mediator on the outcome. To determine the generalizability of these mechanisms and identify subpopulations for whom mediation is most pronounced, we will compare the mediation effects across different subgroups (e.g., higher SES versus lower SES).

The traditional and often-used approach to estimating mediation effects is the causal steps approach, which originated in Baron and Kenny (1986)¹²⁴. However, due to the limitations of that approach, we will estimate the mediation effect using the product of coefficients method¹²⁵. Standard errors will be evaluated using the bootstrap¹²⁶ or the PRODCLIN program¹²⁷. Software exists for sensitivity analysis to violations of sequential ignorability and other assumptions required for causality in mediation analyses^{128,129}. We will apply this software and any additional procedures available to our analyses in order to obtain the most robust and defendable results.

4.8.5 Analyses Corresponding to Aim 3

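### The Aim 2 disparity contrast is inconsistently defined: the text describes a merged comparator, while the effect size and power belong to a pairwise test and the hypothesis names both arms

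*Combined protocol and SAP*

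**What the plan says.** Four places bear on the Aim 2 comparison.

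- **Section 3.2, Aim 2, Hypothesis 1:** "Compared to the Option Grid and usual care arms, the Picture Option Grid will reduce disparities". Both comparators are named.
- **Section 4.8.1, description of the test:** four groups are compared. Two are the Picture Option Grid at each SES level; the other two are "Option Grid and usual care higher SES, Option Grid and usual care lower SES". The paragraph ends by waiving multiplicity adjustment because only one pair of groups is compared in each of Aims 1 and 2.
- **Section 4.8.1, effect and power:** the difference in effect between SES groups "is 8.5 compared to Option Grid or compared to usual care", and "the power for a two-sided alpha-level test at the 0.05-level is just above 80" per cent. The calculation rule is that "power can be conservatively computed as if the patient-level variance was doubled and the total number of patients halved". At 600 participants the plan says that power is unlikely to reach 80%.
- **Section 4.8.4, claim rule:** a reduction in disparity is claimed if the SES effect is "significantly smaller for the Picture Option Grid group than for the other two groups at follow-up".

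Section 4.8.3 (Aim 1) allows a model with one indicator per intervention and adds the interaction of each SES measure with those indicators. It also names Scheffé's method for multiple comparisons.

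**The concern.** Three arms at two SES levels make six groups. Four groups arise only if two arms are merged, and the one-pair argument against multiplicity adjustment also fits only a merged comparator. Section 4.8.6 uses the same grouping for the cost-discussion analysis. An analyst who follows section 4.8.1 literally would therefore test the Picture Option Grid against an average of an active aid and no aid.

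That test does not match Hypothesis 1. A gap that exists only in usual care can make the merged contrast significant, and the result could then be reported as a reduction relative to the Option Grid. Whether pictures narrow the SES gap beyond what a text aid does is the distinctive question of Aim 2. The scenario is plausible: the background in section 3.1.2 cites a review suggesting that decision aids in general narrow such gaps. Nothing in the plan requires significance against each arm separately.

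**Working it through.** **Inputs (section 4.8.1).** "the standard deviation between patients in the intervention arms compared to usual care is 12.00"; "a within-physician intra-class correlation (ICC) of 0.05 is reasonable"; 4 physicians at each of 4 clinics, so 16; attrition 20%; equal allocation to three arms; two-sided alpha 0.05; Aim 2 difference 8.5; variance doubled and N halved.

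**Formulas.** Analysed n = (N/2) × 0.8; cluster size m = n/16; design effect DE = 1 + (m − 1) × 0.05; variance V = 12² × 2 × DE. With a = n/3 per arm, SE(pairwise) = √(V × 2/a) and SE(merged) = √(V × (1/a + 1/(2a))). Power = Φ(difference/SE − 1.96).

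**The plan's figure, N=1,100.** n = 440, m = 27.5, DE = 2.325, V = 669.6, a = 146.7.
- Pairwise: SE = 3.02; Φ(8.5/3.02 − 1.96) = 80.3%. This matches the stated figure.
- Merged: SE = 2.62; Φ(8.5/2.62 − 1.96) = 90.1%. This does not match.

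The same pairwise formula, without the doubling, reproduces the Aim 1 figures for a difference of 9.34: 99.84% at N=1,100 and 80.2% at ICC 0.19; 99.2% and 80.2% (ICC 0.175) for the 550-patient subgroup. One merged variant, a t reference with 8 degrees of freedom, gives 81.1%, but that method does not reproduce the Aim 1 figures.

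**N=600.** n = 240, m = 15, DE = 1.70, V = 489.6, a = 80.
- Pairwise: SE = 3.50; power 68.1%, consistent with the plan's remark that 80% is unlikely to be reached.
- Merged: SE = 3.03; power 80.1%, which would contradict that remark.

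**What the merged test detects.** Let f be the share of the Picture arm's 8.5-point reduction (against usual care) that the Option Grid also achieves. The documents do not give f, so the full range is shown. The merged effect is 8.5 × (1 − f/2); the Picture versus Option Grid effect is 8.5 × (1 − f).

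| f | Merged effect | Merged, N=1,100 | Merged, N=600 | Picture vs Option Grid, N=600 |
|---|---|---|---|---|
| 0 | 8.50 | 90.1% | 80.1% | 68.1% |
| 0.25 | 7.44 | 81.1% | 69.0% | 44.5% |
| 0.5 | 6.38 | 68.3% | 55.7% | 22.8% |
| 0.75 | 5.31 | 52.8% | 41.8% | 8.8% |
| 1 | 4.25 | 36.8% | 28.9% | 2.5% |

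Picture versus usual care alone has 80.3% (N=1,100) and 68.1% (N=600) throughout. At f = 1 the two aids are identical, yet the merged test is significant in favour of the Picture Option Grid 36.8% or 28.9% of the time; a direct test would be so 2.5% of the time.

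**Break-even for power.** SE(merged)/SE(pairwise) = √0.75. The merged test and Picture versus usual care have equal power when 1 − f/2 = √0.75, so f = 2(1 − √0.75) = 0.27.

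**The case against.** The best reply is that the merged comparator is only a parenthesis, and that the rest of the plan points to pairwise contrasts: the effect is worded against either arm, the power figure is pairwise, and the remark about 600 participants fits a pairwise test. The claim rule refers to two groups in the plural. Section 4.8.3 already adds SES interactions with the intervention indicators, and section 4.8.4 carries the linear model over from Aim 1. A direct Picture versus Option Grid comparison in lower-SES women is also pre-specified and powered under Aim 1, Hypothesis 2.

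Much of this stands. A reader might infer that Aim 2 will certainly be analysed with the arms merged; the documents do not establish that. But the pairwise reading leaves the four-group description and the one-pair multiplicity argument unexplained, and no text says that each arm must be beaten. The Aim 1 comparison within lower-SES women is a subgroup effect and not a test of the SES gap.

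Two other strong readings also fail.

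- A reader might infer that merging always loses power against usual care. It does so only if the Option Grid achieves more than about 27% of the Picture arm's reduction. With no Option Grid effect, merging gains power (80.1% against 68.1% at N=600).
- A reader might compute a wrong-claim rate of 47% at N=600 from a within-surgeon variance: SE = √(144 × 0.95 × (2/80 + 2/160)) = 2.27, and Φ(4.25/2.27 − 1.96) = 0.47. That drops the plan's doubled-variance rule and design effect, and assumes that the SES effect does not vary between surgeons. The plan's own method gives 28.9%.

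**Conclusion.** The concern holds as an inconsistency in a pre-specified contrast. Section 4.8.1 describes one test and gives the power of another, and the claim rule in section 4.8.4 does not settle which applies to a hypothesis that names both arms. This is more than missing detail, because the test as literally described can lead to a wrong conclusion: when the Option Grid closes the gap as fully as the Picture Option Grid, it would be significant about 29% of the time at N=600 and 37% at N=1,100.

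These figures rest on the plan's SD, ICC, attrition and variance rule, a normal approximation with equal arms, and a true gap of 8.5 in usual care and 0 under both aids. The rate falls if the gap in usual care is smaller. The point that a merged contrast cannot show superiority to the Option Grid depends on none of these numbers. Aim 2 is secondary, so the trial's primary conclusion is not affected.

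**What to change.** In sections 4.8.1 and 4.8.4, replace the merged comparator by two SES-interaction contrasts from the two-indicator model already allowed in section 4.8.3: Picture Option Grid versus usual care, and Picture Option Grid versus Option Grid. State that a reduction in disparity is claimed only against the arm whose contrast is significant, and that Hypothesis 1 is supported only if both are.

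State the power of each contrast at N=600: about 68% for a true difference of 8.5 on the plan's method, before any multiplicity adjustment. With two contrasts the one-pair argument no longer applies, so delete the multiplicity waiver for Aim 2 or reconcile it with Scheffé's method in section 4.8.3.

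The change is to wording only and needs no new data. Its cost is that a claim against both comparators is harder to meet. The probability that both contrasts are significant cannot exceed the smaller of the two powers, and power against the Option Grid falls to 22.8% at N=600 if the Option Grid achieves half of the reduction.
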